3.2.2 Secondary outcomes

Secondary outcomes of this study include functioning (two items from the Kessler Psychological Distress Scale on days of reduced and lost productivity), perceived sleep quality (1 item from the Pittsburgh Sleep Quality Index [PSQI]), perceived stress level (single item Subjective Level of Stress [SLS-1]), stress coping abilities (Brief Resilience Scale [BRS]) and general self-efficacy (General Self-Efficacy Scale [GSE]). Information about the assessments is summarised in the table provided in Appendix A.

105 106

3.3 Hypotheses

107 108 109

• Those in the LiON group, as compared to the control group, will show greater reductions in (1) depressive and anxiety symptoms, (2) distress symptoms, and (3) perceived stress.

110

Those in the LiON group, as compared to the control group, will also show greater improved (4) functioning, (5) perceived sleep quality, (6) stress coping abilities, and (7) general self-efficacy.

111 112

4. Study design, randomisation, and recruitment

[figure not shown]
113

4.1 Study design and randomisation

This study will adopt an open labelled wait list RCT design (**Figure 1**). Participants will be randomly assigned using a computer-generated sequence into either the (i) low-intensity online intervention (LiON) group (n = 60) or (ii) wait list control (WLC) group (n = 60) in a 1:1 ratio. This study design was adopted to ensure all participants will be able to receive LiON during the period of this study.

Those randomised to the LiON intervention group will first receive the 4-week LiON, with generic self-help tips provided to each participant before completing the T2 assessment. Meanwhile, those randomised to the WLC group will first receive generic self-help tips for a period of 4 weeks, followed by the 4-week LiON before completing the T2 assessment.

Random blocks will be used for randomisation.

^aDuring the review session, the trained interventionist will discuss the concerns and needs of the potential participant to determine the goal of the 4-week LiON sessions, ensure the potential participant meets the inclusion and exclusion criteria of the study, and provide initial briefing about the LiON (including module structure, components of focus).

Figure 1. Flow of the study recruitment and assessment process.

4.2 Details about the process of the RCT and intervention 4.2.1 Before intervention

Prior to the commencement of the LiON, all participants will first be screened for eligibility for participation by a professional clinician of the research team (i.e., psychiatrists or psychologist, senior social worker). An online review session will also be first provided by the trained interventionist (who will be a graduate with background in psychology, social work, or other related mental health disciplines with prior and ongoing training from senior clinicians of the research team) to each participant to determine his or her needs and ensure all inclusion and exclusion criteria are met. Briefing about the LiON, such as module structure and components of focus will also be provided during this session.

4.2.2 The Low-intensity Online Intervention (LiON)

The LiON in the current study is comprised of three core modules identified to be core areas of stress and needs of participants based on clinical experiences of the research team. The three modules include (1) stress management, (2) sleep and relaxation, and (3) problem-solving skills.

 Each module consists of four 1-on-1 sessions which will be conducted through online platforms (such as Zoom). Participants will attend these sessions once a week.

All online modules were designed to target different psychological techniques to manage stress, improve sleep quality and relaxation techniques, as well as improve problem-solving skills.

 Interventionists will guide participants with the support of powerpoint slides to identify session goals and explain psychological techniques and exercises for practising. Worksheets (likened to "homeworks" in CBT) are also given to participants to perform intervention exercises during the session. A copy of the powerpoint slides and additional worksheets will also be provided to participants.

158 159 160

161

162

163

155

156

157

The content of each module is illustrated as follows:

(1) Stress management:

This module aims to guide participants in recognising their source of stress, teach the mechanisms underlying stress and importance of identifying different presentations of stress. The main aim of this module is to provide information about the most recommended models of stress management, and exploring healthy coping strategies.

(2) Sleep and relaxation:

168 169 170 This module focuses on identifying factors impeding participants' sleep and learning relaxation skills. In this module, information on sleep hygiene and relaxation techniques such as quided imagery are provided and practised with participants.

171 172

(3) Problem-solving:

173 174 175

This module is devoted to teaching the importance of dissecting and restructuring problems and doing so by adopting goal-setting models such as SMART model (Strengths, Weaknesses, Opportunities & Threats). Participants will be quided to practice each model with different problems they may face.

176 177

4.2.3 Generic self-help tips

178 179 180

All participants will also be provided with generic self-help tips. For those in the LiON intervention group, these self-help tips will be provided after the 4-week LiON. For those in the WLC group, these self-help tips will be provided during the first 4 weeks after randomisation.

181 182 183

These generic self-help tips will include general advice on what one can do to improve their conditions. Content of these tips may include the following:

184 185

187

- Breathing exercises
- 186
- Exercise Sleep
- 188
- Reduce mobile phone use

Mindfulness-based exercises

189 190 191

4.3 Recruitment and assessment flow

193 194 195

192

Subjects will be recruited via invitations from headwind F20 Subjects will first complete an online screening (including the Kessler Psychological Distress Scale to

196 197 determine distress level). A clinician (e.g., psychiatrist of the research team) will meet the participant through an online platform (such as Zoom) to further conduct a screening of the condition and needs of the participant to determine eligibility and suitability for LiON and the current study. Eligible subjects will be given details about the LiON and presented with the informed consent online

198 199

For participants below the age of 18, parental or quardian consent would be sought online via Qualtrics before proceeding with the study.

200

After consent is sought, participants will be asked to complete the online questionnaire via Qualtrics (at To), which items are listed on Table 1, which can be self-administered (a project staff will be available for the process if requested).

205

Individual randomisation will be conducted through a computer-generated sequence.

206

See **Figure 1** for further details about the flow of recruitment and study design.

207

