3.2 Study outcomes

78 79 80 All measures of this study will be conducted at baseline, i.e., pre-intervention (To), post-intervention (T1), and 1-month follow-up (T2). The time frame will be past month for To assessments and past week for both T1 and T2 assessments. Basic demographics will also be collected at baseline.

81 82

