3.2.1 Primary outcomes

83 84 Primary outcomes of this study include improved symptoms of depression, anxiety, and distress at postintervention (T1) and 1-month follow-up (T2).

85 86

87

88

89

90

Symptoms of depression and anxiety will be assessed using the depression and anxiety subscales (DASS-D and DASS-A, respectively) of the 21-item Depression Anxiety Stress Scale (DASS-21; Lovibond & Lovibond, 1995). The DASS-D and DASS-A each contains 7 items that asks participants about their symptoms of depression and anxiety, respectively, using a 4-point Likert scale (from "did not apply to me at all" [o] to "apply to me very much, or most of the time" [3]). The final score for each subscale was generated by multiplying the sum of the individual items by a value of 2, yielding a score range from 0 to 42, with a higher score indicating higher severity.

95

96

Symptoms of distress will be assessed using 6 items from the Kessler Kessler Psychological Distress Scale (Kessler et al., 2002). Items were rated on a 5-point Likert scale (from "none of the time" [0] to "all of the time" [4]) and summed to generate the final distress score. The total score ranges from 0 to 24, with a high score indicating greater distress.

97 98 99

100

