4.5 Major ethical issues

The study involves participants from a community youth in Hong Kong. The guidelines of handling of personal data such as full name and telephone number will be strictly followed. There is no known hazard or discomfort associated with the semi-structured interviews, online questionnaires via Qualtrics and the intervention, but some participants might not be comfortable with items related to mental illness. Participants are free to withdraw from the study at any tie point without any consequence to their help-seeking psychiatric service. Guardian or parental consent will be required for participants under the age of 18 through online questionnaires via Qualtrics. Information obtained from the consent form will only be accessible by designated research staff. Qualtrics' servers are protected by high-end firewall systems and scans are performed regularly to ensure that any vulnerabilities are quickly found and patched. Application penetration tests are performed annually by an independent third-party. All services have quick failover points and redundant hardware, with backups performed daily.

 Referrals to external health services may be made with the consent of the participants or their guardians or parents if participants are screened to have diagnosable mental disorders. The risks and precautions associated will be explained clearly through the disclaimer and consent process and stipulated in the disclaimer and consent form.

5. Study subjects and sample

Eliqibility of participants is determined according to the following inclusion and exclusion criteria:

5.1 Inclusion criteria:

Inclusion criteria will be (1) **young people aged between 12–30;** (2) who have sufficient proficiency in Chinese to understand verbal and written instructions and give informed consent; (3) with symptoms of mental distress not specific to depressive or anxiety symptoms.

5.2 Exclusion criteria:

Exclusion criteria will be (1) receiving any forms of cognitive behavioural therapy (CBT), (2) active suicidal ideation/attempts within the past one month, (3) inability to turn on camera for the course of the intervention, (4) inability to provide emergency contact, and (5) located outside of Hong Kong.

6. Sample-size and calculation

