The findings of our pilot study (n = 34) suggested that LiON yields an effect size of 0.4 when compared with controls with no intervention at all. To test the main hypothesis that LiON is more effective in reducing participant's distress level than online self-help tips, we estimate the effect size could be halved, with alpha = 0.05 and power = 80%, 52 subjects are needed for each group totalling 104 subjects. After accounting for a 15% attrition, we target 120 subjects for the current study.

7. Statistical Analysis

All statistical analyses will be carried out using IBM® SPSS® with the significance level set at 0.05. Repeated measure ancova model will be used to compare the changes of distress level between two groups with adjustment for the variables that exhibit baseline differences.

A planned analysis will take place after data is available for the first 60 subjects, to provide a more accurate estimate of the power of the study to adjust the final sample size and allocation to the study arms, according to the principles of adaptive trial design.

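### The screening Kessler score is a second pre-randomisation measure of distress with no planned role in the distress analysis; naming it as a covariate could buy a modest gain in precision

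*Protocol*

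**What the plan says.** - **Screen.** Protocol section 4.3: "Subjects will first complete an online screening (including the Kessler Psychological Distress Scale to" establish how distressed the person is. A clinician then judges eligibility. The section does not give the number of items, the recall window, or the interval to T0.
- **T0.** Later in section 4.3: "After consent is sought, participants will be asked to complete the online questionnaire via Qualtrics (at To"). Section 3.2 confirms that every measure is repeated: "All measures of this study will be conducted at baseline, i.e., pre-intervention (To), post-intervention (T1), and 1-month follow-up (T2"). Section 3.2.1 makes Kessler distress a primary outcome beside DASS-D and DASS-A: "Symptoms of distress will be assessed using 6 items from the Kessler Kessler Psychological Distress Scale".
- **Randomisation.** Section 4.3 lists it after the T0 questionnaire: "Individual randomisation will be conducted through a computer-generated sequence".
- **Recall.** Section 3.2: "The time frame will be past month for To assessments and past week for both T1 and T2 assessments".
- **Entry criterion.** Section 5.1 asks for people "with symptoms of mental distress not specific to depressive or anxiety symptoms" and gives no Kessler cut-off.
- **Analysis.** Section 7: "Repeated measure ancova model will be used to compare the changes of distress level between two groups". Adjustment is limited to variables that turn out to differ between the arms at baseline. The same section plans an analysis once data on the first 60 subjects are available.

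**The concern.** By the order of section 4.3, each enrolled participant has answered a Kessler measure twice before allocation. A six-item self-report score is a noisy reading of a person's usual distress. A second reading taken before randomisation can explain further outcome variance, and treatment cannot have affected it.

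The covariate rule in section 7 gives the screening score no planned use. It would be adjusted for only if the arms happened to differ on it, and prognostic value plays no part. It may not even be a candidate, since section 3.2 equates baseline with T0. At stake is some precision in the distress comparison, which is the hypothesis behind the sample size. The first post-intervention visit (T1) matters most, because under section 4.1 the control arm also receives LiON before T2.

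**Working it through.** **Inputs from the protocol.** Section 6 gives 52 per group, 104 in total, 15% attrition and a target of 120. Evaluable participants are then 120 × 0.85 = 102.

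**The plan's own figure.** With effect size 0.2 read as a standardised mean difference, two-sided alpha 0.05 and 80% power, n per group = 2 × ((1.960 + 0.842)/0.2)², which is 393 and not 52. The unhalved 0.4 gives 99. The 52 is not reproduced on this reading. That is a separate matter, but it limits what a precision gain can achieve. The target of 120 equals 104 × 1.15; dividing by 0.85 gives 123.

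**Assumed inputs.** The protocol gives no correlations. Let r0 and rs be the correlations of the T0 and screening scores with the T1 score, and r the correlation between T0 and screen. The reference model is an ANCOVA with T0 as the only baseline covariate. Section 7 does not say that T0 enters this way, so the reference is itself an assumption.

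**Formulas.**
- T0 alone: R² = r0².
- T0 and screen: R² = (r0² + rs² − 2·r0·rs·r)/(1 − r²).
- Ratio of residual variances = (1 − R² with both)/(1 − r0²).
- Equivalent extra participants = 102/ratio − 102.

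| r0, rs, r | R², T0 alone | R², both | Ratio | Variance cut | Extra on 102 |
|---|---|---|---|---|---|
| 0.6, 0.6, 0.7 | 0.360 | 0.216/0.51 = 0.424 | 0.901 | 9.9% | about 11 |
| 0.5, 0.5, 0.7 | 0.250 | 0.150/0.51 = 0.294 | 0.941 | 5.9% | about 6 |
| 0.5, 0.45, 0.7 | 0.250 | 0.1375/0.51 = 0.270 | 0.974 | 2.6% | about 3 |
| 0.5, 0.45, 0.8 | 0.250 | 0.0925/0.36 = 0.257 | 0.991 | 0.9% | about 1 |
| 0.5, 0.35, 0.7 | 0.250 | 0.1275/0.51 = 0.250 | 1.000 | 0% | 0 |

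The gain vanishes when rs = r0 × r, as in the last row (0.5 × 0.7 = 0.35).

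**Cost of the extra covariate.** Residual degrees of freedom fall from 102 − 3 = 99 to 98, a loss of about 1/99, or 1%. This cancels the 0.9% case and turns the last row into a very small loss.

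**Sensitivity.** If the two pre-randomisation readings agree no better with each other than with the T1 score, the gain is larger: 11.1% with all correlations at 0.5 and 19.8% with all at 0.8. Two readings of one scale before treatment would usually agree better than that, so I do not rely on these cases.

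**Effect on power.** If the T0-only model had exactly 80% power, a 5.9% cut would raise it to 82.3% and a 9.9% cut to 83.9%. At a standardised difference of 0.2 with 52 per group and the second row's correlations, power goes from 21.7% to 22.8%. At 0.4 it goes from 65.4% to 68.0%.

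**The case against.** The strongest objection is that this is a matter for the SAP, which is not shown, and that one baseline per outcome is ordinary practice. A reader might infer from section 4.3 that the screening score serves only for entry and is then discarded. The protocol does not say so: it states one purpose and excludes no other. That part of the objection stands. What remains is that section 7 is not silent on covariates. It states a rule, and under that rule the score has no planned place.

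Four further limits also stand.
- The same-instrument premise is incomplete. Section 4.3 names the Kessler scale without an item count, and its recall window and timing relative to T0 are not given. The order of events is taken from the text, because Figure 1 was not available for this check.
- The magnitude rests on assumed correlations and an assumed reference model. Selection on distress at the screen would narrow the range of the score and shrink the gain.
- A reader might call the precision free. The screen precedes consent and, for those under 18, parental consent, so research use of the score needs cover. The consent form was not in the text reviewed and may already provide it.
- The screen is not stated to include the DASS, so DASS-D and DASS-A gain no second baseline.

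**Conclusion.** The point holds as a low-cost improvement and not as an error that threatens the trial. Two Kessler measures precede randomisation in the text, and the section 7 rule would use the first only if the arms happened to differ on it. Naming both in advance is valid whatever the correlations.

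The likely benefit over T0 alone is roughly 0 to 10% less residual variance, or about 0 to 11 participants on 102, before the 1% cost of the extra covariate. This assumes correlations of 0.5 to 0.6 between T0 and T1, 0.35 to 0.6 between screen and T1, and 0.7 to 0.8 between screen and T0.

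The tempting inference that this would rescue the power of the trial is not supported: at a standardised difference of 0.2, power at 52 per group moves by about one percentage point in the 5.9% case.

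**What to change.** In section 7, state that the distress model adjusts for the T0 Kessler score and the screening Kessler score whether or not the arms differ on them. T0 then enters as a covariate and not also as a repeated outcome level. Fix this before the analysis at 60 subjects.

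Keep the item-level screening responses. If the screen contains the same six items, score those; otherwise use the screening total as its own covariate.

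The mean of the two scores is an alternative that saves a degree of freedom, but it needs a common scale and forces equal weights. With correlations 0.5, 0.35 and 0.7 and equal variances, its R² is (0.5 + 0.35)²/(2 × 1.7) = 0.213, below the 0.250 from T0 alone. Two separate covariates are therefore the safer choice.

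Make sure consent, including parental consent, covers research use of the screening data. The total cost is a sentence in the analysis section, one consent line and one degree of freedom, for a gain that may prove to be nil.

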4.4 Minimisation and avoidance of bias

Participant blinding is not possible in a psychological intervention study. Randomisation will be carried out via a computer-generated sequence. To minimise differential expectations in the different conditions, descriptions of the different arms of the study will be presented to subjects in a neutral and descriptive language in the online informed consent form.

4.5 Major ethical issues

The study involves participants from a community youth in Hong Kong. The guidelines of handling of personal data such as full name and telephone number will be strictly followed. There is no known hazard or discomfort associated with the semi-structured interviews, online questionnaires via Qualtrics and the intervention, but some participants might not be comfortable with items related to mental illness. Participants are free to withdraw from the study at any tie point without any consequence to their help-seeking psychiatric service. Guardian or parental consent will be required for participants under the age of 18 through online questionnaires via Qualtrics. Information obtained from the consent form will only be accessible by designated research staff. Qualtrics' servers are protected by high-end firewall systems and scans are performed regularly to ensure that any vulnerabilities are quickly found and patched. Application penetration tests are performed annually by an independent third-party. All services have quick failover points and redundant hardware, with backups performed daily.

 Referrals to external health services may be made with the consent of the participants or their guardians or parents if participants are screened to have diagnosable mental disorders. The risks and precautions associated will be explained clearly through the disclaimer and consent process and stipulated in the disclaimer and consent form.

5. Study subjects and sample

Eliqibility of participants is determined according to the following inclusion and exclusion criteria:

5.1 Inclusion criteria:

Inclusion criteria will be (1) **young people aged between 12–30;** (2) who have sufficient proficiency in Chinese to understand verbal and written instructions and give informed consent; (3) with symptoms of mental distress not specific to depressive or anxiety symptoms.

5.2 Exclusion criteria:

Exclusion criteria will be (1) receiving any forms of cognitive behavioural therapy (CBT), (2) active suicidal ideation/attempts within the past one month, (3) inability to turn on camera for the course of the intervention, (4) inability to provide emergency contact, and (5) located outside of Hong Kong.

6. Sample-size and calculation

The findings of our pilot study (n = 34) suggested that LiON yields an effect size of 0.4 when compared with controls with no intervention at all. To test the main hypothesis that LiON is more effective in reducing participant's distress level than online self-help tips, we estimate the effect size could be halved, with alpha = 0.05 and power = 80%, 52 subjects are needed for each group totalling 104 subjects. After accounting for a 15% attrition, we target 120 subjects for the current study.

7. Statistical Analysis

All statistical analyses will be carried out using IBM® SPSS® with the significance level set at 0.05. Repeated measure ancova model will be used to compare the changes of distress level between two groups with adjustment for the variables that exhibit baseline differences.

A planned analysis will take place after data is available for the first 60 subjects, to provide a more accurate estimate of the power of the study to adjust the final sample size and allocation to the study arms, according to the principles of adaptive trial design.

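### At the 15% attrition the protocol assumes, 120 randomised leaves 102 evaluable (51 per arm), two short of the 104 it says are needed

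*Protocol*

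**What the plan says.** Section 6 (Sample-size and calculation) gives the requirement before dropout: "52 subjects are needed for each group totalling 104 subjects". The next sentence makes the allowance for dropout: "After accounting for a 15% attrition, we target 120 subjects for the current study". No formula is given for the step from 104 to 120.

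Section 4.1 carries the total into the design as 60 in the LiON arm and, for the comparator, "wait list control (WLC) group (n = 60) in a 1:1 ratio".

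Section 7 plans an analysis once data on the first 60 subjects are available, to re-estimate power and adjust the final sample size and the allocation.

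**The concern.** Attrition is a fraction of those randomised, so the number to randomise is the evaluable number divided by one minus the attrition rate. Adding the same percentage to the evaluable number gives too small a total. The stated target is what that shortcut produces.

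At stake is whether the trial, at its own assumed dropout, reaches the number it says it needs. The numerical consequence here is slight, but the error is on the optimistic side. If the shortcut was used, it would carry into any later revision of the sample size: at 15% it yields 1.15 × 0.85 = 0.9775 of the required evaluable number, a shortfall of 2.25% whatever the starting figure.

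**Working it through.** **Inputs, all from the protocol.** Evaluable number needed: 52 per group, 104 in total (section 6). Attrition: 15% (section 6). Target to randomise: 120 (section 6), as 60 + 60 (section 4.1). Alpha 0.05 and power 80% (section 6); whether the test is one- or two-sided is not stated.

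**1. Reproducing the stated target.**
- Multiplying: 104 × 1.15 = 119.6, which rounds up to 120. This matches.
- Dividing: 104 / (1 − 0.15) = 104 / 0.85 = 122.4, which rounds up to 123. Per arm, 52 / 0.85 = 61.2, so 62 per arm and 124 in total. Neither matches.

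**2. What 120 delivers at 15% loss.**
- Total: 120 × 0.85 = 102.
- Per arm: 60 × 0.85 = 51.
- Shortfall: 104 − 102 = 2, one per arm.

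**3. The attrition that 120 does cover.**
- 1 − 104/120 = 0.133, or 13.3%.

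**4. Effect on power.** The protocol does not state an effect size and metric from which 52 per group can be recovered, so this step works backwards from 52. Assume a two-sample t-test, two-sided 0.05, with 52 the smallest per-arm number that reaches 80%.
- The standardised difference with exactly 80% power is 0.555 at 52 per arm and 0.560 at 51 per arm. If 52 is the smallest sufficient number, the design effect lies between these two values.
- Power at 51 per arm is 79.2% if the effect is 0.555 and 80.0% if it is 0.560.
- The loss against the stated 80% is therefore at most about 0.8 percentage points.

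**5. Chance of keeping at least 104.** Assume that each subject drops out independently with probability 0.15.

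| Randomised | Expected evaluable | P(at least 104 evaluable) |
|---|---|---|
| 120 | 102.0 | 36% |
| 123 | 104.6 | 62% |
| 124 | 105.4 | 69% |

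The correct totals also miss 104 fairly often, because an attrition allowance fixes the expected number and does not guarantee it. The 36% should be read only beside the other two rows.

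**The case against.** The case on the other side concerns weight, since the subtraction itself is not in dispute.

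- **Size.** Two subjects in 104 and under one point of power will not change the trial's conclusion. This stands, and it is why the point is minor.
- **Mechanism.** A reader might infer that the protocol documents a multiplication by 1.15. It does not; no formula appears. The match with 119.6 makes it likely, but 122.4 could also have been brought down to a round 120. The inconsistency between 104, 15% and 120 holds either way.
- **Power.** A reader might conclude that the trial loses its 80% power, or that power is 79.2%. The documents do not support either. The figure is the lower end of a range of 79.2% to 80.0%, and it rests on an effect of about 0.555 that the protocol never states.
- **The larger question about 52.** Section 6 reports that "LiON yields an effect size of 0.4 when compared with controls with no intervention at all" and then halves this value. If 0.2 is read as a standardised mean difference (the metric is not stated), power is about 17% with either 51 or 52 per arm, and the attrition slip is immaterial beside that. This is a separate matter. Correcting the attrition step would not settle it, and re-deriving 52 would not correct the attrition step.
- **The planned adjustment.** Section 7 allows the total to change after the first 60 subjects, so 120 is an initial target and a gap of two could be absorbed there. That is fair, provided that the adjustment handles attrition correctly. It does not make the sentence in section 6 right.

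**Conclusion.** Wrong as written, low severity. The figures 104 needed, 15% attrition and 120 randomised cannot all hold: 120 covers 13.3% attrition, or leaves 102 evaluable at 15%. That conclusion follows from the protocol's own numbers and needs no assumption about the effect size, the test or the number of sides. Nothing elsewhere in the protocol corrects it.

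The size is two evaluable subjects. The translation into power (a loss of at most about 0.8 points) does rest on assumptions: a two-sided t-test, and 52 per arm as the smallest number giving 80%. It takes 52 per group as given and is no endorsement of that figure. The finding does not show that the trial is materially underpowered, and it gives no reason by itself to recruit more subjects.

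**What to change.** Keep 120 and restate the sentence in section 6 in one of two ways:

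- *120 randomised allows for about 13% attrition while retaining 104 (52 per group)*; or
- *120 randomised leaves 102 evaluable (51 per group) after 15% attrition*.

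The second wording should not carry a power figure for 51 per group unless the effect size and its metric are stated, because power cannot be computed without them.

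For the adjustment planned in section 7, specify that the number to randomise is the evaluable number divided by (1 − attrition).

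The cost is one corrected sentence and one added formula, with no extra recruitment and no change to the design. The only downside is that the stated allowance, or the stated evaluable number, becomes slightly less favourable.

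### The protocol names three primary scales at two visits but sizes and models distress only, with 0.05 for every analysis and no order among the primaries

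*Protocol*

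**What the plan says.** Protocol section 3.2.1 sets the primary outcomes: "Primary outcomes of this study include improved symptoms of depression, anxiety, and distress at postintervention (T1) and 1-month follow-up (T2". The first two are scored separately: "Symptoms of depression and anxiety will be assessed using the depression and anxiety subscales (DASS-D and DASS-A, respectively". Distress is a third score, the sum of six Kessler items. That makes three scales at two visits.

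Section 6 has a single target: "To test the main hypothesis that LiON is more effective in reducing participant's distress level than online self-help tips". The group size follows from that hypothesis alone: "with alpha = 0.05 and power = 80%, 52 subjects are needed for each group totalling 104 subjects".

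Section 7 names one model, also for distress: "Repeated measure ancova model will be used to compare the changes of distress level between two groups". All analyses are run "with the significance level set at 0.05".

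Sections 3.1 and 3.3 list the outcomes side by side, depression and anxiety ahead of distress, without a ranking. Section 4.1 has the wait-list arm receive self-help tips for four weeks and then LiON, before the T2 assessment.

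**The concern.** Section 3.2.1 cannot be squared with sections 6 and 7. Either distress alone is primary and section 3.2.1 claims too much, or all three scales are primary and sections 6 and 7 neither size nor model two of them.

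Three things hang on the answer:

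- **Error rate.** With several primaries, each at 0.05 and unranked, the chance of some false-positive primary result exceeds 0.05.
- **Choice of conclusion.** The protocol does not fix which result carries the conclusion. That matters more in an open-label trial with self-completed questionnaires.
- **The look at 60 subjects.** Section 7 plans to re-estimate power then, and to adjust sample size and allocation. With the primary unsettled, it is unclear which outcome's power governs that decision.

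**Working it through.** **1. The sections side by side**

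| Section | Outcome | Visit |
|---|---|---|
| 3.2.1 | DASS-D, DASS-A, 6-item distress | T1 and T2 |
| 6 | distress level | not named |
| 7 | change in distress level | not named (repeated measures) |

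Three scales × two visits = 6 primary combinations. Sections 6 and 7 cover one scale.

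**2. The plan's own figures**

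The protocol gives no familywise error rate to reproduce. Its only related figure is 52 per group, from a pilot effect of 0.4 that is then halved ("we estimate the effect size could be halved"). Read as a standardised mean difference of 0.2, two-sided: n = 2(1.960 + 0.842)²/0.2² = 392.4, so 393 per group, not 52. Read as Cohen's f = 0.2 with two uncorrelated measurements, the total is 102, close to 104. The protocol states neither reading. This is a separate matter and does not enter the false-positive rates below.

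**3. Error rate for k independent tests**

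The level of 0.05 is from section 7; two-sided testing is assumed, because the protocol does not state it.

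- Either direction, 1 − 0.95^k: k = 3 gives 1 − 0.8574 = 14.3%; k = 6 gives 1 − 0.7351 = 26.5%.
- In LiON's favour only, 1 − 0.975^k: k = 3 gives 7.3%; k = 6 gives 14.1%. A single test gives 2.5%.

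**4. Error rate for correlated tests**

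The protocol gives no correlations, so a range is assumed. Under no effect anywhere, the test statistics are drawn as multivariate normal (400,000 draws). The correlation between two different scales at two different visits is the product of the scale and visit correlations. The table shows the share of draws with any |Z| > 1.96, and in brackets the share with any Z > 1.96 in LiON's favour.

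| Scales / visits | One test per scale (3) | Six tests |
|---|---|---|
| 0 / 0 | 14.3% (7.3%) | 26.5% (14.1%) |
| 0.5 / 0.5 | 12.5% (6.3%) | 21.9% (11.1%) |
| 0.7 / 0.5 | 10.8% (5.4%) | 19.2% (9.6%) |
| 0.7 / 0.7 | 10.8% (5.4%) | 17.6% (8.8%) |
| 0.8 / 0.8 | 9.8% (4.9%) | 14.9% (7.4%) |

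The visit correlation plays no part in the three-test column.

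**5. Which visit answers section 6**

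Section 6 contrasts LiON with self-help tips. Under section 4.1 that contrast exists only up to T1; by T2 both arms have been given LiON. Three of the six combinations, those at T2, therefore do not test the main hypothesis.

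**The case against.** The strongest reply is that section 6 already names a main hypothesis. If distress is the sole primary with a single test, the error rate is 5% and there is no inflation. A repeated-measures model may also give one test per scale rather than one per visit, and a SAP that is not shown may hold a multiplicity rule.

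Much of this stands. A reader might infer that six tests will each be judged at 0.05 and that any one of them makes the trial positive, with a false-success rate of about 19–25%. The protocol does not support that as a statement of fact:

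- It does not say that six separate tests will be run.
- It states no success rule.
- The 19–25% range needs particular correlations that it does not give.
- That range counts differences in either direction, whereas the hypotheses in section 3.3 favour LiON.

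Nor is the lack of an adjustment method a fault in itself, since a SAP commonly supplies one.

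What the reply does not remove is the contradiction. Section 3.2.1 declares three primary scales at two visits, and sections 6 and 7 treat one. A rule in a SAP would leave both statements in the protocol.

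**Conclusion.** The point holds as an internal contradiction about the primary question. It is firm because it rests on stated text.

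Its size is conditional. If every primary is tested at two-sided 0.05 and any one result could support a positive conclusion, the chance of at least one false-positive primary result is about 10–14% for three tests and about 15–26% for six. In LiON's favour it is about 5–7% and 7–14%, against 2.5% for one test. The ranges cover assumed correlations from 0 to 0.8. If distress at one test is the only primary, the rate is 5% and nothing is inflated; the protocol should say so.

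**What to change.** In sections 3.2.1 and 7, name one primary endpoint in line with the main hypothesis of section 6: the 6-item distress score defined in section 3.2.1, compared between arms at T1, two-sided 0.05. Sections 6 and 7 mention neither the six items nor T1, so both must be written in, and section 7 should say that the T1 contrast is the primary result of the model. T1 is proposed because it is the only visit that compares LiON with self-help tips.

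Make DASS-D and DASS-A at T1 key secondary outcomes, tested after the primary in a fixed order or by Holm. The other secondary outcomes can stay as specified. Settle this before the look at 60 subjects, so that its power estimate refers to the named endpoint.

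The cost is wording, and depression and anxiety carry less formal weight. No new data or participants are needed.

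The alternative is to keep all three scales as primaries at T1 with Holm. That controls the error equally well, but the sample-size basis must be restated. Holm's first step is at 0.05/3 = 0.0167 (critical value 2.394). A scale with 80% power at 0.05 has Φ(2.802 − 2.394) = 66% power there. Restoring 80% takes (2.394 + 0.842)²/(1.960 + 0.842)² = 1.33 times the participants.
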